Phase I Study of Panobinostat Plus ICE Chemotherapy Followed by A Randomized Phase-II Study of ICE compared with Panobinostat Plus ICE For Patients With Relapsed and refractory Classical Hodgkin Lymphoma

1.0 OBJECTIVES:

1.1 Primary objective:

- Phase-I: To determine the maximal tolerated dose (MTD) of panobinostat + ICE combination
- Randomized Phase-II: To estimate the complete response (CR) rate in patients with relapsed and refractory classical HL receiving ICE versus PANOBINOSTAT (LBH589) plus ICE therapy

1.2 Secondary Objectives:

- To assess the safety and tolerability of the novel combination of PANOBINOSTAT (LBH589) plus ICE versus ICE in patients with relapsed and refractory HL
- To estimate the overall response rate (CR + PR)
- To estimate the success rate of stem cell collection in patients eligible for stem cell transplant
- To estimate the percentage of patients who subsequently undergo autologous stem cell transplantation (ASCT)
- To estimate the event free survival (EFS) at 1 year after randomization
- To determine pretreatment expression level of HDAC1, HDAC2, and pSTAT3 and pSTAT6 by IHC and correlate the results with treatment response

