6.1 Pre-Treatment Evaluation

Within 30 days (+/- 7 days) of starting therapy

- 6.1.1 Imaging studies (a chest x-ray (CXR), CT scans of the head and neck, chest and abdomen and pelvis, and a PET scan).
- 6.1.2 Bone marrow biopsy, if clinically indicated.
- 6.1.3 Serum HIV test if the patient has risk factors or did not have one within the past 12 months.
- 6.1.4 ECHO/MUGA
- 6.1.5 Medical History Assessment

Within 7 days (+/- 2) of starting therapy

- 6.1.7 CBC with differential, chemistry (albumin, BUN, glucose, ALT/SGPT, AST/SGOT, alkaline phosphatase, LDH, total bilirubin, creatinine, sodium, potassium, calcium, magnesium)
- 6.1.8 EKG
- 6.1.9 Physical examination, vital signs and weight
- 6.1.10 Serum pregnancy test for females of child bearing potential

6.2 Evaluation During The Study:

- Within 7 days of starting each cycle of ICE therapy: physical examination, CBC with differential, SMA and electrolytes.
- Blood (about 2 1/2 teaspoons) will be collected for routine tests.
- Weekly CBC, and electrolytes while on study.
- Toxicity evaluation within 7 days of each ICE therapy.
- Repeat imaging studies after 3 cycles of ICE. (7-13 days after completion of ICE)
- Bone marrow biopsy (if it was positive before starting therapy) and PET scan should be performed to confirm CRs
- EKG 1 (+/- 2 days) per table 6.3
-
- All patients who receive at least one dose of panobinostat will be evaluable for response and toxicity unless the reason for premature termination of the study is reasons other than progression or toxicity (such as poor compliance or patient withdrawal).
- The patient completes the study upon response evaluation with PET scan after 3 cycles of treatment, unless toxicity of grade 3 or greater related to the treatment is ongoing, in which case until it is resolved.

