9.1 Duration of Treatment and Patient Participation

- Patients will receive 3 cycles of ICE (phase II only) or ICE + PANOBINOSTAT (LBH589) (phase I or phase II). Responding patients who are transplant eligible will be removed from the study and offered standard of care stem cell collection regimens. Non-responding patients will be offered alternative management plan by the treating physician.

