Patients' demographic characteristics at baseline including age, gender, and race will be analyzed, with categorical variables summarized in frequency tables while continuous variables summarized using mean (\pm s.d.) and median (range). The student t-test/Wilcoxon test will be used to compare continuous variables between different patient groups. The chi-square test or the Fisher's exact test will be applied to assess the association between two categorical variables. Complete remission rate along with its 95% CI will be estimated for each treatment arm. Logistic regression will be utilized to assess the effect of patient demographic factors and treatment on CR.

Time-to-event outcomes, including event-free survival (EFS), duration of response, and overall survival (OS), will be estimated using the Kaplan-Meier method. The log-rank test will be performed to test the difference in time-to-event distributions between patient groups. Cox proportional hazards model will be used to include multiple covariates in the time-to-event analysis.

Serum levels of TARC and biomarkers of interest such as HDAC1, HDAC2, pSTAT3, and pSTAT6 by IHC at baseline and change from baseline to post-treatment will be evaluated for each treatment arm. We will study the association between markers and CR using logistic regression models, and the association between markers and time-to-event outcomes using Cox proportional hazards models.

Toxicity data will be summarized by frequency tables. The association between both type and severity of toxicity and the treatment groups will be evaluated. No formal statistical testing will be performed on these summary data.

11.0 DATA AND PROTOCOL MANAGEMENT:

Data will be collected by a research nurse, and will be recorded in the PDMS Data Management System.

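### The study ends at the PET after cycle 3, yet 1-year EFS, stem cell collection, transplant and survival outcomes are planned with no efficacy follow-up and no EFS definition

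*Combined protocol and SAP*

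**What the plan says.** **When participation ends.** Section 6.2: "The patient completes the study upon response evaluation with PET scan after 3 cycles of treatment". The one exception it allows is for severe (grade 3 or worse) treatment-related toxicity that has not yet cleared. Section 9.1: "Responding patients who are transplant eligible will be removed from the study and offered standard of care stem cell collection regimens". The same section sends non-responders to management chosen by the treating physician and mentions no further study contact.

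**What is to be estimated.** Section 1.2 lists as a secondary objective "To estimate the event free survival (EFS) at 1 year after randomization". It also lists the success rate of stem cell collection and the percentage of patients who go on to autologous transplant. The Analysis Plans in Section 10.0 add: "Time-to-event outcomes, including event-free survival (EFS), duration of response, and overall survival (OS), will be estimated using the Kaplan-Meier method". Log-rank tests and Cox models follow, including "the association between markers and time-to-event outcomes using Cox proportional hazards models".

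**Nearest related text.**
- Section 6.2.1 describes one end-of-treatment or withdrawal visit (examination, weight, vital signs, EKG). It allows some patients who benefit but cannot be transplanted to stay on study, with approval. It gives them no efficacy assessments.
- Section 8.0 defines relapse or progression for response assessment and does not link it to EFS.
- Section 9.2 follows adverse events for 30 days after the last dose. Section 12.0 covers serious adverse events, deaths during participation and pregnancies.
- Section 10.0 mentions a website field for last evaluation date and patient status. Section 11.0 names the data system. Both say where data are kept, not what is collected or until when.

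**The concern.** A stated end-of-study rule conflicts with stated objectives, so this is more than a missing detail. Under the rule:

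- 1-year EFS needs observation for about ten months beyond the last planned assessment.
- Duration of response starts at the very visit that ends participation, so a responder who completes there contributes no planned follow-up to it.
- Collection and transplant in transplant-eligible responders happen after those patients have been removed.
- Overall survival has no planned source after the short safety window.

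If follow-up existed, the EFS estimate would still be undefined. The plan does not say whether death, start of new therapy or failure to respond counts as an event, or whether transplant is an event, a censoring point or neither. In a population treated with transplant as the goal, that choice can change the estimate materially.

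**Working it through.** **1. The plan's own timing.** Section 10.0 places the response evaluation at 3 cycles, given as 2 months. The table of operating characteristics measures trial length to the last patient's response evaluation. Subtracting accrual time (average N divided by 3 per month) from the stated length gives the time left after the last enrolment:

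| Scenario | Average N | N/3 (months) | Stated length (months) | Remainder (months) |
|---|---|---|---|---|
| 1 | 31.2 + 30.8 = 62.0 | 20.7 | 23.1 | 2.4 |
| 2 | 19.1 + 32.8 = 51.9 | 17.3 | 18.8 | 1.5 |
| 3 | 14.2 + 25.7 = 39.9 | 13.3 | 14 | 0.7 |
| 4 | 18 + 31.7 = 49.7 | 16.6 | 17.9 | 1.3 |

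No scenario leaves anything near 12 months. The design was sized and timed to the response evaluation.

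**2. Day of the response PET, counted from ICE day 1.** Inputs: three cycles of 14 days (Section 5.2.6), so cycles start on days 1, 15 and 29; etoposide on days 1 to 3 (Table 5.2); imaging 7 to 13 days after completion of ICE (Section 6.2); removal if an ICE delay exceeds 14 days (Section 5.2.7).

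- If completion means the last ICE drug: 29 + 2 = day 31, and 31 + 7 to 31 + 13 = days 38 to 44.
- If completion means the end of cycle 3: 29 + 13 = day 42, and 42 + 7 to 42 + 13 = days 49 to 55.
- With both intervals between cycles delayed by the full 14 days (the limit read as applying to each delay): 55 + 28 = day 83.
- The 2-day window on each interval moves either end by up to 4 days: 38 - 4 = day 34, and 83 + 4 = day 87.

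The plan's 2 months lies inside this range.

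**3. Share of the EFS year.** 38/365 = 10.4% and 83/365 = 22.7%. Days left: 365 - 38 = 327 and 365 - 83 = 282.

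Counted from the first panobinostat dose (day -6, 7 days before ICE day 1), the PET falls on days 45 to 90. That is 45/365 = 12.3% to 90/365 = 24.7%, with 320 to 275 days left.

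**4. Calendar cost of a full year.** At 70 patients and 3 per month, accrual takes 70/3 = 23.3 months. The last response evaluation falls at 23.3 + 2 = 25.3 months, and the last patient's 12-month point at 23.3 + 12 = 35.3 months. The difference is 10 months.

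**5. Does the primary design depend on any of this?** The stated adaptive design was re-simulated with a 2-month response lag and nothing after the PET (1,500 trials per scenario). The probability of selecting panobinostat plus ICE came out at 0.109, 0.570, 0.844 and 0.639 for Scenarios 1 to 4. The table gives 0.122, 0.573, 0.859 and 0.638. The primary design runs on the response evaluation alone.

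**The case against.** The strongest reply is that Sections 6.2 and 9.1 end on-protocol evaluation, while progression, transplant and death can still be read from medical records later. That is plausible, and nothing in the documents forbids it. A reader might otherwise infer that 1-year EFS can never be estimated. The documents do not support that. They support only that the plan does not say how these outcomes will be obtained, for whom, until when, or by what definition.

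Second, Section 8.0 supplies a usable progression criterion, and Section 12.0 records deaths during participation and late related serious events. This stands as far as it goes: progression need not be defined afresh. It still gives no schedule, no EFS event list and no censoring rule.

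Third, Section 6.2.1 lets some patients stay on study, so the PET is not an absolute cap. This is correct for a subset whose size and time on study are not stated. It leaves out transplant-eligible responders, to whom the collection objective and much of the transplant objective apply.

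Two further inferences go too far. One is that incomplete follow-up would differ between arms. Section 9.1 sets the same path for both arms, so this is a possibility and not a finding. The other is a count of patients who would happen to reach 12 months of observation before the trial closes. Such a count needs status to be kept current for everyone until then, which the documents do not say.

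**Conclusion.** The point holds for the secondary objectives and analyses, and the sponsor should correct it. For patients who complete at the PET, planned efficacy observation ends at about day 38 to 83 from ICE day 1 (34 to 87 with the scheduling window), roughly 10% to 23% of the first year. The plan as written does not support 1-year EFS, duration of response or overall survival. Collection and transplant outcomes of transplant-eligible responders fall after removal from study.

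The percentages assume that randomization is close to the start of treatment, since the interval is not given. They describe the protocol PET and not the patients continued under Section 6.2.1.

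A reader might extend the criticism to the primary comparison. That is not supported: complete response is assessed at the PET itself, and the adaptive randomization and its stopping rules use nothing later.

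**What to change.** In Sections 6.2 and 9.1, separate the end of protocol treatment from the end of study follow-up, and reconcile both with Section 6.2.1. Who continues treatment is for the protocol team to decide.

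Add text such as: *All randomized patients in both arms are followed to at least 12 months after randomization, whether or not they are receiving protocol treatment.* Abstract these items from records:

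- stem cell collection result
- date of transplant
- progression by the Section 8.0 criteria
- start of new therapy
- death
- date of last contact

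In Section 10.0, define EFS events and censoring, and state how transplant and new therapy are handled.

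If these data will not be collected, delete the 1-year EFS objective and the EFS, duration of response and overall survival analyses, including the marker Cox models. The collection and transplant objectives can stay, because each needs only one item from the record.

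**Cost.** A protocol amendment; record abstraction for up to 70 patients, some of them possibly managed elsewhere by then; and about 10 more months before the secondary analyses (35.3 against 25.3 months at full accrual). The primary analysis need not wait. The consent pages are not available here, so whether consent wording must change cannot be judged.

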6.2.1 End-of-Treatment Visit (after completing 3 cycles of ICE) or Withdrawal visit

- Physical exam, including measurement of your weight and vital signs.
- EKG

Patients who benefit from the study drug or the combination, if not eligible for stem cell transplant (SCT), should be allowed to continue on study with the approval of principal investigator (PI) and the attending physician.

6.3 Cardiac assessments

A screening 12-lead ECG will be performed to assess study eligibility. Additional 12-lead ECGs will be performed at a minimum at scheduled time points as indicated in Table 6-3.

Table 6-3: Cardiac assessment monitoring schedule

Cycle	Day of cycle	ECG monitoring
Screening		Single ECG to assess eligibility
Cycle 1	-6	Single pre-dose ECG
	-6	Single Post-dose (2 ± 0.5 hours)
	-2	Single pre-dose ECG
	-2	Single Post-dose (2 ± 0.5 hours)
Cycle 2 and all subsequent cycles	1	Single pre-dose ECG
End of treatment	Last	Single ECG

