Arm 3: Patients in Arm 3 were assigned to a dosing regimen of three-times-a-week every other week (q.o.w.). The first cohort in Arm 3 was treated at a dose level of 30 mg three-times-a-week q.o.w and the second cohort at 45 mg three-times-a-week q.o.w. Two patients were treated in cohort 2 and both

patients experienced a DLT in the first cycle. The dose level of 30 mg was determined to be the MTD for Arm 3.

Arm 5: Patients in Arm 5 were assigned to 30 mg, 45 mg or 60 mg dose of oral panobinostat given twice-a-week every week. In the 60 mg cohort, 1 patient was evaluable, and this patient experienced a DLT. As such, the MTD was determined to be 45 mg for Arm 5.

Human pharmacokinetics

After oral administration, panobinostat is rapidly absorbed with no observed lag phase. Maximum plasma concentrations were generally reached within 1 hour after oral dosing. The absolute bioavailability was 30% (data on file) and the mean (SD) half-life of panobinostat was comparable following i.v. and oral dosing ~15.0 (5) hours. Moderate drug accumulation was observed with oral three-times-a-week schedule but not with the weekly i.v. schedule (1.4-fold drug accumulation with oral three-times-a-week dosing), consistent with the terminal half-life of 15 hours and dosing interval.

Figure 0-1 Mean panobinostat plasma concentration versus time profiles following single oral or intravenous administration

[figure not shown]

Table 0-2 Pharmacokinetic parameters of panobinostat in three ongoing Phase I studies [CLBH589A2101], [CLBH589B2101], and [CLBH589B2102]

Route of administration & Dose (No. of patients following single dose)	Mean (CV%) Single dose C _{max} (ng/mL)	Mean (CV%) Single dose AUC _{0-inf} (ng*hr/mL)	Mean (CV%) Multiple dose AUC ₀₋₄₈ (ng*hr/mL)
i.v. 20 mg/m ² (n=31)	784 (45)	1041 (38)	n/a
p.o. 20 mg (n=45)	22.8 (58)	194 (58)	258 (65)
p.o. 30 mg (n=49)	36.2 (62)	267 (54)	279 (54)
p.o. 40 mg (n=24)	58.0 (59)	329 (77)	270 (59)
p.o. 60 mg (n=57)	66.1 (68)	362 (62)	306 (50)
p.o. 80 mg (n=18)	63.5 (58)	397 (49)	369 (52)
n/a: not applicable with weekly i.v. administration			

In vitro experiments suggested that the hepatic oxidative metabolism of panobinostat is mediated

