ECG abnormalities were also evidenced during serial monitoring and central adjudication of their tracings. T-wave abnormalities (flat, inverted or biphasic T-waves) and ST segment depressed were the most frequent ECG abnormalities increasing in frequency by increasing the dose of panobinostat. The ECG abnormality table reports abnormalities with a cut-off of 5% in dose groups with n ≥ 25 patients having a 5% cutoff and of 25% when n < 25 patients in a given dose group.

Relationship between panobinostat plasma concentrations and QTcF

As presented in Figure 1-3 (i.v.) and Figure 1-4 (po) below, the maximum change of QTcF from baseline does not coincide with the peak plasma concentration-time course of panobinostat for either route of administrations suggesting a possible delayed effect. It is noteworthy (as shown in Table 1-3) that the mean maximum concentration (C_{max}) and overall exposure (AUC) for the oral formulation is at least 30-fold and 5-fold, respectively lower than that has been seen with intravenous panobinostat. It does not appear that QTcF change is directly related to panobinostat plasma concentrations.

Figure 0-2 QTcF change from baseline over time vs. panobinostat conc-time course following the first intravenous panobinostat weekly doses

[figure not shown]
[figure not shown]

Figure 0-3 QTcF change from baseline over time vs. panobinostat conc-time course following the first oral panobinostat doses of a MWF schedule

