5.1.3 Phase-I dose levels

Panobinostat + ICE combination therapy will be administered at the dose level assigned to each cohort, as outlined in Table 5. Each ICE cycle is considered to be 14 days (2 weeks). A tumor response assessment will be done within 7-13 days of completion of 3 cycles of ICE using the Revised Response Criteria for Malignant Lymphoma. Patients with a complete response (CR) or partial response (PR) will be considered for stem cell transplantation, otherwise they will be removed from the study.

Table-5: Study design for the phase-I		
Dose Level	ICE chemotherapy Day 1 and repeat every 14-days	PANOBINOSTAT (mg, orally) 3 times per week
-1	See Table 5.2	10
0	See Table 5.2	20
1	See Table 5.2	30

5.1.4 Panobinostat is given only during cycles 1 and 2 of ICE according to Table 5.1. Cycle 3 of ICE will be given without panobinostat.

5.1.5 Investigational therapy: Panobinostat (LBH589).

Panobinostat will be provided by Novartis. Oral Panobinostat will be supplied as 5-mg or 20-mg hard gelatin capsules.

Medication labels will comply with US legal requirements and be printed in English. They will supply no information about the patient. The storage conditions for study drug will be described on the medication label.

During the study, Panobinostat will be self-administered (by the patients themselves) orally three times per week.

For cycle 1 of ICE: Panobinostat will be administered starting day -6 and ICE on day 1 as outlined in Table 5.1:

Patients should be instructed to take their oral dose of Panobinostat around the same time each day. Each dose of Panobinostat should be taken with an 8 oz / 240 ml glass of water. Patients should be instructed to swallow the capsules whole and not chew them. Patients must avoid grapefruit or grapefruit juice and seville (sour) oranges during the entire study.

If the patient forgets to take his/her dose on a scheduled treatment day, then he/she should take Panobinostat on that same day within 12 hours after the missed dose if possible. After more than 12 hours, that day's dose should be withheld, and the patient should wait to take Panobinostat until the next scheduled treatment day (i.e., patients should be instructed not to try to make-up the missed dose after 12 hours). The patient should then continue treatment with the original dosing schedule. A pill diary will be provided to the subject for documentation of dosing for each cycle.

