5.1.11 Dose Elimination/Holding/Reduction

A scheduled dose of panobinostat may be held no more than 3 consecutive doses in a 2 week cycle of ICE and no more than 6 consecutive doses in a 3 week cycle of ICE. If it is held longer than this specified time, that patient will be removed from study.

For example, if a patient is delayed 1 week to receive a cycle of ICE then 6 consecutive doses of panobinostat may be missed but if ICE is administered every 2 weeks on schedule then no more than 3 consecutive doses of panobinostat may be missed.

For those patients entered in the expanded cohort (Dosing Schedule B) of adjusted panobinostat dosing, panobinostat will be self administered by patient 3x/week starting D-6 and will continue through D5 and be held until start of next cycle of ICE. If ICE is held due to AE and given every 3 weeks, a patient cannot miss more than 6 consecutive doses of panobinostat or will be removed from study.

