Cycle 1 day -6 and -2 only, post-dose:	A single post-dose ECG obtained shows QTcF \geq 480 msec to $<$ 500 msec OR > 60 msec increase from baseline	
If abnormality noted on Day 6 or -2 of Cycle 1 (post- dose):
 
Check and correct the patient's serum potassium, magnesium, calcium and phosphorus immediately, as well as evaluate con-meds.
 
Monitor ECG hourly or by telemetry until at least 2 consecutive hourly ECGs performed at least 6 hours post dose are $<$480.
 
Notify Investigator immediately for prompt review. Delay dose 3 days and repeat pre-dose ECG.
 
If the pre-dose ECG:
 
Do not meet pre-dose ECG criteria for dosing (pre-dose ECGs have a QTcF \leq 460 msec), discontinue patient from study.
 
Do meet pre-dose ECG criteria for dosing (pre-dose ECGs have a QTcF \leq 460 msec) and QT prolongation determined to be related to study drug, resume study drug treatment with a dose reduction of 10 mg. If however, it was determined that the QT prolongation was secondary to electrolyte abnormalities or con-meds, continue at the same dose level. Repeat ECGs - pre-dose (x3), 3-hours post-dose (x3), and 6-hours post-dose (x3) on the next scheduled dosing day after the reduced dose is given*.

	A single ECG obtained shows QTcF \geq 500 msec	
Check and correct the patient's serum potassium, magnesium, calcium and phosphorus immediately.
 
Notify Investigator immediately for prompt review.
 
Discontinue patient from study therapy

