
Antibiotics
 
Macrolide antibiotics*
 
 • erythromycin • clarithromycin • telithromycin 
Quinolone antibiotics*
 
sparfloxacin

Antipsychotics
 
thioridazine
 
mesoridazine
 
chlorpromazine
 
pimozide

Antimalarials 
• halofantrine• chloroquine
Miscellaneous drugs 
• arsenic trioxide• astemizole• bepridil• domperidone• levomethadyl• methadone• pentamidine• droperidol
*Note: azithromycin, ciprofloxacin, levofloxacin, pefloxacin, ofloxacin, tosufloxacin, difloxacin, temafloxacin, fleroxacin, acrosoxacin, nalidixic acid and enoxacin are allowed.

This is not a comprehensive list of medications which may prolong the QT interval or have a risk of causing Torsades de pointes. This list of medications was developed in collaboration with an external cardiology consultant, and represents those medications which are deemed to have an unacceptable risk of co-administration with panobinostat.

The following website may be referenced as a supplemental guide for drugs which have been associated with Torsades de pointes or prolonging the QT interval but at this point lack substantial evidence for causing Torsades de pointes:

<http://www.qtdrugs.org/medical-pros/drug-lists/drug-lists.htm#>.

Medications listed on the website which do not appear in [Table 1-1](#) above may be used with caution at the discretion of the investigators.

The serotonin (5HT₃) antagonists, often used as antiemetics, such as ondansetron dolasetron, (also are known CYP2D6 substrates, see [Table 3-1](#)), or granisetron have been associated with Torsades de points and QT prolongation but have not been shown to cause Torsades de pointes. Therefore, 5HT₃ antagonists are not per se prohibited but close monitoring for signs and symptoms of QT prolongation is recommended. Caution is to be exercised when using these or other agents that may prolong QT intervals in combination with panobinostat.

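### No scheduled ECG follows a panobinostat dose given with ICE, and the cycle 3 day 1 ECG precedes no panobinostat dose

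*Combined protocol and SAP*

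**What the plan says.** Section 6.3 makes Table 6-3 the minimum: "Additional 12-lead ECGs will be performed at a minimum at scheduled time points as indicated in Table 6-3". The table lists a screening ECG, a pre-dose and a 2-hour post-dose ECG on each of days -6 and -2 of cycle 1, one pre-dose ECG on day 1 of cycle 2 and of every later cycle, and one at end of treatment. The post-dose row of Table 7-2 has the same limit: "Cycle 1 day -6 and -2 only, post-dose".

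Panobinostat starts on day -6 and ICE on day 1 (Section 5.1.5, Tables 5.1 and 5.1.1). Under Schedule A, cycle 1 dosing runs to day 12. Under Schedule B, Section 5.1.11 says that panobinostat "will continue through D5 and be held until start of next cycle of ICE", and Table 5.1.1 shows day 5 as the last dose. On the third cycle, Section 5.1.4 says: "Cycle 3 of ICE will be given without panobinostat". Section 5.2.4 repeats this for phase II.

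On the drug, Section 3.1 gives a mean half-life of 15 h (SD 5 h). It says that the largest QTcF change "does not coincide with the peak plasma concentration-time course of panobinostat for either route of administrations suggesting a possible delayed effect". Appendix 1 says of 5HT3 antagonists that "close monitoring for signs and symptoms of QT prolongation is recommended".

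**The concern.** The trial tests panobinostat together with ICE. The dose-limiting toxicity (DLT) window in Sections 5.1.6, 5.1.7 and 5.1.13 runs for 14 days from the first ICE dose, and with few exceptions any non-hematologic toxicity of grade 3 or more counts (Section 5.1.9). Symptomless QTcF prolongation can count only if someone records an ECG.

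The documents treat the risk as real. Section 3.1 reports grade 3 QTcF as a DLT in one patient at 80 mg in an earlier panobinostat study. It also reports QTcF above 500 ms in 3 of 158 patients with hematologic malignancies, one of them at 20 mg, which is dose level 0 here. If every scheduled ECG is taken before ICE starts or days after the last panobinostat dose, the ECG data describe panobinostat alone and its aftermath, and say little about the period of joint dosing.

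**Working it through.** There is no stated figure to reproduce. The check puts doses and ECGs on one day axis. Tables 5.1 and 5.1.1 include a day 0. With the 14-day cycle of Section 5.1.3, cycle 2 day 1 is day 15 and cycle 3 day 1 is day 29.

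**Days.** I assume that cycle 2 repeats the dosing days from day 1 on, without the lead-in.

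| | Schedule A | Schedule B |
|---|---|---|
| Lead-in doses | -6, -4, -2 | -6, -4, -2 |
| Cycle 1 doses from day 1 | 1, 3, 5, 8, 10, 12 | 1, 3, 5 |
| Cycle 2 doses | 6 | 3 |
| All doses | 15 | 9 |
| Doses on or after first ICE day | 12 | 6 |
| Of these, with a scheduled post-dose ECG | 0 | 0 |

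**Gap between ECGs.** The last cycle 1 ECG is 2 h after the day -2 dose. ICE starts 3 × 24 − 2 = 70 h later. The next ECG, on day 15, comes 17 × 24 − 2 = 406 h after that last one. Days 1 to 14 contain none.

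**Time since the last dose at the cycle 2 day 1 ECG.** Half-lives elapsed = hours / half-life; fraction left = 2^(−half-lives).

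- Schedule B, day 5 to day 15: 240 h. 240/15 = 16.0 half-lives, 0.0015% left. At 20 h it is 12.0; at 10 h, 24.0.
- Schedule A, day 12 to day 15: 72 h. 72/15 = 4.8 half-lives, 3.6% left. At 20 h it is 3.6 half-lives (8.2%); at 10 h, 7.2 (0.7%).

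**Sensitivity to the half-life.** Section 3.1 reports 1.4-fold accumulation. For dosing every 48 h, accumulation = 1/(1 − 2^(−48/half-life)). A half-life of 15 h gives 1.12. A value of 1.4 needs about 26.6 h. Schedule B then gives 240/26.6 = 9.0 half-lives (0.19% left) and Schedule A 72/26.6 = 2.7 (15% left).

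**Cycle 3.** Table 6-3 calls the day 1 reading pre-dose, but Sections 5.1.4 and 5.2.4 give no panobinostat in that cycle. Table 7-2 nevertheless lists cycle 3 day 1 among the readings that decide whether study drug is delayed, resumed 10 mg lower or stopped. A reduction in milligrams fits panobinostat; the ICE doses are set by body surface area or AUC.

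**The case against.** A reader might infer that QT is not monitored during the combination. The documents do not support that. The day 1 ECGs of cycles 2 and 3 each follow a full combined cycle, and the cycle 2 reading decides whether panobinostat is given. There is an end-of-treatment ECG, weekly electrolytes (Section 6.2), a screening QTc limit (Section 4.3), a bar on the Appendix 1 drugs (Section 7.3) and triplicate repeats after an abnormal reading. Table 6-3 is a minimum. All of this stands. But the minimum guarantees no further ECG, electrolytes do not measure QT, and the repeats need an abnormal scheduled ECG to trigger them.

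A reader might also take 16 half-lives to mean that the cycle 2 reading carries no QT information. That goes too far. The figure holds only for Schedule B at the mean half-life. Section 3.1 also finds no direct relation between QTcF change and concentration, so washout is an imperfect measure of QT information.

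Nor should the 10 days be stretched to 17 by adding the one-week ICE delay of Section 2.5. That delay arose under continuous panobinostat dosing, and no delay rate is given for Schedule B.

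The documents report no QT effect of ICE, so an added combination effect is a hypothesis. The 2-hour reading already lies after the peak, which Section 3.1 places within 1 hour. Whether it misses the QTcF maximum cannot be judged here, because the oral QTcF figure is not shown. The 3-hour and 6-hour ECGs in Table 7-2 are follow-up after an abnormal reading, not a rival routine schedule.

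Finally, Section 6.2 allows 2 days either side for the ECG, which could be read to place the cycle 2 reading after the day 1 dose. The pre-dose label in Table 6-3 and its role in Table 7-2 argue against that reading.

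**Conclusion.** The point holds as a gap in the schedule. At nominal times, 0 of 6 panobinostat doses given from the first ICE day on (Schedule B), or 0 of 12 (Schedule A), are followed by a scheduled post-dose ECG, and days 1 to 14 of the DLT window have no scheduled ECG. These counts rest on the day tables and 14-day cycles, not on any half-life. The distance from the last dose to the next ECG depends on the schedule: 10 days under B and 3 under A. Section 2.5 keeps both schedules open, while Table 5.2 names B for phase II.

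The cycle 3 day 1 entry is a separate inconsistency: a pre-dose reading with no panobinostat dose to precede, tied to study-drug decisions. This does not show that the MTD would be wrong or that patients are without cardiac safeguards. It shows that a small rearrangement would let the trial observe QTcF under the combination it tests.

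**What to change.** Move the cycle 3 day 1 ECG to a post-dose reading on a day when panobinostat and ICE are both given. Cycle 1 day 3 is one example: it is a panobinostat day in both schedules, and the patient receives intravenous etoposide that day. Over three cycles the count stays at 8 (screening 1, cycle 1 four, cycle 2 one, cycle 3 one, end of treatment 1), with the cycle 3 ECG now in cycle 1.

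Reconcile Table 6-3, the ECG window in Section 6.2 and both parts of Table 7-2 with the Schedule B dosing in Section 5.1.11 and Table 5.1.1, including the cycle 3 reference in Table 7-2. State why 2 hours was chosen for the post-dose ECGs, given the possible delayed effect in Section 3.1. The sponsor chooses the post-dose time; no action limit or dosing rule is proposed here.

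The cost is a short amendment, a slightly longer stay on one treatment day, and the loss of the scheduled reading between cycle 2 panobinostat and cycle 3 ICE. That loss matters more under Schedule A, where the reading comes 3 days after the last dose, than under Schedule B, where it comes 10 days after.
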